7.3 Adverse Events

All summaries of adverse events will be based on treatment-emergent adverse events. Adverse events will be provided in a listing. The number and percentage of subjects experiencing adverse events will be summarized. Summaries by maximum severity and relationship to the study device (active or sham) will also be provided. Serious adverse events and adverse events leading to discontinuation from the study will be presented. Treatment-related adverse events will be defined as adverse events with investigator assessment of related or possibly related. In summaries of adverse events by severity and relationship to study device, patients reporting multiple episodes will be counted once under the worst severity and the strongest relationship, respectively. Serious adverse events will also be presented by relationship to treatment. The number of patients with at least one adverse event will be tabulated for each treatment group. The number of adverse events for each treatment group will also be tabulated.

7.4 Sample Size

This is a Phase III study with a sample size of 170 patients (85 per treatment group). The sample size for the trial has been set at 170. Based on a previously conducted clinical trial assessing the efficacy and safety of the Provant Therapy System in a similar population, the mean \pm standard deviation change in the NPRS from baseline to 60 days was 1.79 ± 1.83 units. The data are derived from the open-label, single arm part of the trial in which all subjects received PEMF. Assuming a placebo effect of 40% results in an assumed between group difference of 1.07 units. Based on alpha = 0.05 and 90% power, a sample size of 62 patients per treatment group would be needed based on a two-sided sample t-test for the NPRS. A total sample size of 162 was estimated based on an assumed premature discontinuation rate of 30%.

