	At Month 11 , subjects will receive a telephone call to ensure treatment compliance, and to assess safety and concomitant medication changes. Subjects will be reminded to record ePRO data for one week prior to the 361-day (Month 12) end of study visit.
	At Month 12 (end of open-label treatment extension), subjects will return to the clinic for evaluation of safety, weight, QST, NCS, TCNSS, PGI, treatment satisfaction, review of device usage (reports will be supplied to the site) and collection of diary data, concomitant medication changes, quality of life outcomes (NeuroQoL), and will return the study device. Subjects who consented and had biopsies collected at the 4 Month visit, will have their end of study biopsies performed during this visit. Biopsy samples will be sent directly to the central laboratory for assessment.
Sample Size	The anticipated enrollment in this study is 170 subjects. The estimate of 85 patients per arm is based on results from a previous trial of PEMF therapy in this patient population.
Study Locations	Up to 20 sites in the United States
Indication	Adjunctive treatment of diabetic neuropathic pain and discomfort.
Visit Schedule	This study includes a total of 8 clinic visits and 7 telephone calls. The visit schedule is as follows:
	• Screening Visit (Day -15)
	• Enrollment Visit (Day 0)
	• Day 7 phone call (+2 days)
	• Month 1 (± 3 days)
	• Month 2 (\pm 3 days)
	• Month 3 (± 3 days)
	• Month 4 (± 3 days) (end of Part A / start of Part B)

	• Month 6 phone call (± 3 days)
	• Month 7 phone call (± 3 days)
	• Month 8 Visit (± 3 days)
	• Month 9 phone call (± 3 days)
	• Month 10 phone call (± 3 days)
	• Month 11 phone call (± 3 days)
	• Month 12 Visit (end of Part B) (± 3 days)
Treatment Arms	Part A - 1:1 Randomization (PEMF 42 μs : Sham) Part B – open-label PEMF 42 μs treatment
Efficacy Endpoints	 Primary Endpoint: Absolute change from baseline in pain intensity as measured by the 11-point, numerical pain rating scale (NPRS) (0-10; where 0=no pain, to 10=worst possible pain) through 4 months.

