Ho: μ (Change in NPRS score at 4 months / PEMF group) = μ (Change in NPRS score at 4 months / sham group)

Ha: μ (Change in NPRS score at 4 months / PEMF group) $\neq \mu$ (Change in NPRS score at 4 months / sham group)

To compare the absolute change in pain from baseline to 4-months, the intra-patient change will be calculated and serve as the dependent variable in the analysis. The baseline pain score will be introduced in the model as a covariate. Clinical site will be added to the model to assess poolability of the data across sites. Interaction between clinical site and treatment will be evaluated using a type 1 error rate of 10%.

Mixed Models with Repeated Measures (MMRM) comparing results across all time-points will also be performed, adjusted for the baseline value, week, treatment by week interaction and the effect of the patient.

Sub-group analysis will be pre-specified in the SAP and will be performed on subjects with pain scores ≥ 5 as well as subjects with A1C above and below 8.5.

Missing or Incomplete Data

If a patient reports at least 3 days with non-missing pain intensity scores within a particular week, the weekly mean pain intensity score will be derived using the non-missing scores only. This is identical to imputing the missing scores as the mean of the non-missing scores. If the patient reports less than 3 days with non-missing pain intensity scores within a particular week, the weekly mean pain intensity score will be treated as missing data.

Missing weekly mean pain intensity scores will be imputed using multiple missing data and pattern mixture methodology. Sensitivity analyses will be conducted exploring different patterns for missing data. An MMRM will be performed using only observed data without multiple imputation

and an analysis using the change from baseline to the last non-missing weekly mean pain intensity score will also be provided.

The pattern mixture model methodology will be implemented using SAS procedures MI and MIANALYZE. Specifically, the following steps will be followed:

• Intermittent missing data will first be imputed using the Markov Chain Monte Carlo (MCMC) method implemented with the SAS MI procedure, which is appropriate for non-monotonic missing data.

Data for patients who discontinues early will be multiply imputed as follows:

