4.3. Sample Size Justification

This is a Phase III study with a sample size of 170 patients (85 per treatment group). The sample size for the trial has been set at 170. Based on a previously conducted clinical trial assessing the efficacy and safety of the Provant Therapy System in a similar population, the mean \pm standard

November 7, 2018

deviation change in the NPRS from baseline to 60 days was 1.79 ± 1.83 units. The data are derived from the open-label, single arm part of the trial in which all subjects received PEMF. Assuming a placebo effect of 40% results in an assumed between group difference of 1.07 units. Based on alpha = 0.05 and 90% power, a sample size of 62 patients per treatment group would be needed based on a two-sided sample t-test for the NPRS. A total sample size of 162 was estimated based on enrolling 1.3 times the target sample size of 124 patients (124 * 1.3 = ~162).

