7.2. Handling of Dropouts or Missing Data

Missing data may have an impact upon the interpretation of the trial data. Values for missing data will not be imputed, however a methodology is defined for missing dates. All available data for subjects who do not complete the study will be included in the data listings. An analysis of the last recorded observation will be conducted to facilitate a comparison predicated on the ITT population.

Safety Data

Missing or incomplete data will not be imputed. For patients who withdraw from the study prematurely, the last recorded observation will serve as final observation.

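### The 162 that Protocol 7.4 ties to 30% discontinuation covers only about 23% loss; 30% loss needs 178, and the planned 170 covers 27%

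*Protocol*

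**What the plan says.** Protocol 7.4 starts from an earlier trial of the device: mean NPRS change 1.79, SD 1.83, reduced by an assumed 40% placebo effect to a difference of 1.07. It concludes: "Based on alpha = 0.05 and 90% power, a sample size of 62 patients per treatment group would be needed". The test it names for this step is a two-sided t-test. It then says "A total sample size of 162 was estimated based on an assumed premature discontinuation rate of 30" per cent.

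SAP 4.3 repeats these inputs but ends differently: "A total sample size of 162 was estimated based on enrolling 1.3 times the target sample size of 124 patients". It prints the multiplication by 1.3 and states no discontinuation rate.

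Both sections fix enrolment at a third number. In the protocol's words, "The sample size for the trial has been set at 170", that is, 85 per group. The synopsis explains it only by saying that "The estimate of 85 patients per arm is based on results from a previous trial of PEMF therapy in this patient population".

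**The concern.** If a fraction d of those enrolled is lost, keeping n evaluable takes n/(1 − d) enrolled. Multiplying n by (1 + d) gives too few, and the gap widens as d grows. The SAP's printed arithmetic is the second calculation, while the protocol presents its result as if it came from the first.

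Two things follow. The protocol claims protection against a loss that 162 cannot absorb. The planned 170 is also left without a derivation: no text explains the step up from 162 or ties 170 to a loss rate, and the previous trial's figures, to which the synopsis refers, lead to 62 per arm. Someone judging whether the primary comparison survives the attrition the sponsor itself assumed would be misled by 7.4 and would have to work out the tolerance of 170 unaided.

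**Working it through.** **Inputs** (Protocol 7.4, repeated in SAP 4.3 except for the 30% rate): mean change 1.79; SD 1.83; placebo effect 40%; two-sided alpha 0.05; power 90%; t-test; 62 per group; totals 162 and 170. The 30% discontinuation rate is in Protocol 7.4 only. Allocation is 1:1 (Protocol 3.6).

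**1. The evaluable number reproduces.** Difference = 1.79 × (1 − 0.40) = 1.074, printed as 1.07. The normal approximation, n = 2(1.960 + 1.282)² × (1.83/1.07)² = 61.5, rounds up to 62 per group. The exact two-sample t calculation (noncentrality difference/(SD·√(2/n)), 2n − 2 degrees of freedom) needs 61.99 per group at 1.074 and 62.45 at 1.07. Power at 62 per group is 90.0% and 89.8% respectively. So 62 per group, 124 in total, stands.

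**2. The inflated number reproduces only as a multiplier.**
- 124 × 1.3 = 161.2, rounded up to 162, as in SAP 4.3.
- 124/(1 − 0.30) = 177.1, rounded up to 178 for equal groups (89 each).
- 178 − 162 = 16; 178 − 170 = 8.

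**3. Loss each total can absorb before falling below 124.**
- 162: 162 − 124 = 38, and 38/162 = 23.5%.
- 170: 170 − 124 = 46, and 46/170 = 27.1%.
- A 30% loss is 48.6 of 162, or 51 of 170.

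**4. Power at 30% loss** (exact t-test, SD 1.83, discontinued subjects contributing nothing):

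| Enrolled | Evaluable | Per group | Power, difference 1.07 | Power, difference 1.074 |
|---|---|---|---|---|
| 162 | 113.4 | 56.7 | 87.0% | 87.2% |
| 170 | 119.0 | 59.5 | 88.6% | 88.8% |
| 178 | 124.6 | 62.3 | 89.9% | 90.1% |

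**5. Sensitivity to baseline adjustment.** The planned primary model is not the unadjusted t-test: "The baseline pain score will be introduced in the model as a covariate". The documents give no correlation between baseline and change, so any value is an assumption. With residual SD = 1.83 × √(1 − r²), power at 30% loss returns to 90% when r is about 0.20 to 0.22 for 170 enrolled, or 0.29 to 0.31 for 162. The ranges cover differences of 1.074 and 1.07. Below those values a shortfall remains.

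**The case against.** The best counter-argument is that 162 is only an intermediate figure. Enrolment is 170, so the gap to 178 is 8 subjects, not 16, and power at 30% loss is about 1.2 points below the same calculation at 62 per group. That is correct and limits the consequence. It does not remove the error, because 162 is the only inflated total either document ties to a calculation, and 170 does not cover 30% either.

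It is also fair that SAP 4.3 is correct as written, since it claims only a multiplier, and that a reader can compute 1 − 124/170 unaided. The faulty sentence is in the protocol. The synopsis statement is incomplete rather than false.

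A further objection is that discontinued subjects are not simply dropped from the analysis. Protocol 7.1 plans multiple imputation and MMRM; SAP Section 11 keeps the MMRM; and SAP 7.2 says "An analysis of the last recorded observation will be conducted to facilitate a comparison predicated on the ITT population". True power could therefore differ from the table in either direction. But SAP 7.2 also rules out imputing missing values, so the documents disagree on how such subjects are kept. The protocol's own inflation step treats them as lost. Neither retention nor baseline adjustment makes 162 an allowance for 30% loss.

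**Conclusion.** The concern holds. The link in Protocol 7.4 between 162 and 30% discontinuation is wrong: 162 covers 23% loss, and 30% needs 178. The two documents give different justifications for the same number, and neither gives one for 170. The planned 170 tolerates 27% loss and has 88.6% to 88.8% power at 30%. This assumes a difference of 1.07 to 1.074, an SD of 1.83, no information from discontinued subjects and an unadjusted t-test. It is an error of statement with a modest effect, worth correcting but no reason to call the trial underpowered.

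**What to change.** Keep 170. Delete the sentence in Protocol 7.4 that ties 162 to 30% discontinuation, and use the same text there and in SAP 4.3, for example:

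> 124 evaluable subjects (62 per group) give 90% power for a difference of 1.074 (0.6 × 1.79) and SD 1.83. Randomizing 170 keeps at least 124 if discontinuation is at most 27%. At 30% discontinuation (119 evaluable) power is about 89%, assuming that discontinued subjects contribute no data and an unadjusted t-test.

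Giving the unrounded 1.074 matters because 62 per group falls just short of 90% at 1.07. Have the synopsis sentence on 85 per arm refer to this text.

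The cost is wording only, with no change to enrolment or analysis. The stated power at 30% discontinuation becomes about 89% instead of 90%. Holding 90% at that rate would take 178, eight more subjects than planned, which a gain of about one point does not justify.

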8. INFORMED CONSENT

It is the responsibility of the investigator, or a person designated by the investigator (if acceptable by local regulations), to obtain written informed consent from all subjects prior to participating in this study. The original informed consent from will be filed in the Investigator Site File.

If new safety information results in significant changes in the risk/benefit assessment, the consent form will be reviewed and updated if necessary. All subjects (including those already being treated) will be informed of the new information, given a copy of the revised form and be re-consented to continue in the study.

9. INSTITUTIONAL REVIEW BOARD

This protocol, the informed consent form and any accompanying material provided to the subject (such as subject information sheets or descriptions of the study used to obtain informed consent) as well as any advertising or compensation given to the subject, will be submitted by the investigator or investigator's designee to an IRB. Approval from the IRB must be obtained before starting the study and should be documented in a letter to the investigator specifying the date on which the IRB met and granted the approval.

10. TERMINATION OF THE INVESTIGATION

As the study sponsor, Regenesis Biomedical, Inc. reserves the right to terminate the study at any time. Should early termination be necessary, Regenesis Biomedical, Inc. and the investigator will consult and make sure that adequate consideration is given to the protection of subjects' interests.

Additionally, all clinical investigational data will be reviewed by the sponsor on a regular basis. Reports of all data will be made available to the Institutional Review Boards and to the FDA as required. Unanticipated adverse device events will be evaluated and reported in accordance with 21 CFR Part 812 requirements and as required by the governing IRB.

The clinical investigation will be suspended if the investigator or the sponsor, upon review and evaluation of the clinical data, finds the severity or incidence of single or total adverse events unacceptable for continuation of the investigation.

11. ADVERSE EVENTS AND UNANTICIPATED ADVERSE DEVICE EFFECTS

11.1 Adverse Events

An adverse event is defined as follows: Any untoward medical occurrence in a patient or clinical investigation patient administered a medical device treatment which does not necessarily have to have a causal relationship with this treatment. An AE can therefore be any unfavorable and unintended sign (including an abnormal laboratory finding), symptom, or disease temporally associated with the use of study device treatment, whether or not considered related to the study device.

All AEs occurring after signing of the consent form will be recorded. AEs arising subsequent to the time of initiation of first treatment with study device will be considered treatment emergent AEs.

At each contact with the subject, the investigator or designee must seek information on AEs by nonleading specific questioning and, as appropriate, by examination. All observed or volunteered AEs, regardless of suspected causal relationship to study device, must be recorded in the patient's chart.

Any events involving illnesses or injuries with onset during the study or any events involving exacerbations of pre-existing illnesses should be recorded. All clearly related signs and symptoms should be grouped together and recorded as a single diagnosis in the patient's chart. A pre-existing condition must not be reported as an AE unless the condition worsens during the trial.

Each AE will be independently judged by the investigator in terms of causality. The following definitions will be used for these causality assessments.

Related:	This causal relationship is assigned when the AE:
	• starts a reasonable time after study device administration,
	• cannot be reasonably explained by the subject's clinical state.
Possibly Related:	This causal relationship is assigned when the AE:
	• starts a reasonable time after study device administration, but
	• could have been produced by the subject's clinical state or other modes of therapy administered to the subject.
Unrelated:	This causal relationship is assigned when the AE:
	• is definitely not associated with the study device administered and is readily explained by other events or diagnoses.

Each AE will also be independently judged by the investigator in terms of severity. The following definitions will be used for these severity assessments.

Mild:	The event is transient (<48 hours) or causes mild discomfort; no medical intervention/therapy is required
Moderate:	The event results in mild to moderate limitation in activity – some assistance may be needed; no or minimal medical intervention/therapy is required
Severe:	The event results in marked limitation in activity, assistance is usually required; medical intervention/therapy is required and hospitalization is possible

Each AE will also be independently judged by the investigator in terms of seriousness. A serious adverse event (SAE) is defined as any untoward medical occurrence that:

- Results in death, or
- Is life-threatening,

Note: The term "life-threatening" in the definition of "serious" refers to an event in which the subject was at risk of death at the time of the event; it does not refer to an event which hypothetically might have caused death if it were more severe.

- Requires inpatient hospitalization or prolongation of existing hospitalization,
- Results in permanent impairment of a body function or permanent damage to a body structure,
- Is a congenital anomaly/birth defect,

• Necessitates medical or surgical intervention to preclude any one of the outcomes listed in this definition.

All SAEs must be reported *immediately* (within 24 hours of knowledge of the event) by telephone and fax to the study manager:

[contact] Attention: Medical Monitor

The investigator will follow up with a written description of the SAE submitted to the sponsor within 3 days, including the results of the SAE investigation and any treatment(s) provided.

All adverse events will be followed until resolution or until the investigator assesses the subject's status has returned to normal.

11.2 Anticipated Adverse Device Effects Associated with Provant Therapy System

Anticipated adverse events associated with PROVANT® Therapy System are as follows:

- Skin Reaction in the application area (i.e. rash, erythema)
- Altered sensation in the treatment area (i.e. burning, paresthesia)
- Hyperalgesia in the application area (i.e. increased pain, hypersensitivity)

11.3 Unanticipated Adverse Device Effect (UADE)

Unanticipated Adverse Device Effect means any serious adverse effect on health or safety or any life-threatening problem or death caused by, or associated with, a device, if that effect, problem, or death was not previously identified in nature, severity, or degree of incidence in the protocol or informed consent form, or any other unanticipated serious problem associated with the device that relates to the rights, safety, or welfare of subjects. The protocol will contain all of the anticipated Adverse Events that could be associated with the study.

All UADEs must be reported *immediately* (within 24 hours of knowledge of the event) by telephone and fax to the following:

Regenesis Biomedical, Inc. [contact]The investigator will follow up with a written description of the UADE submitted to the sponsor within 3 days, including the results of the UADE investigation and any treatment(s) provided.

Any UADE occurring up to the date of the final Follow-up Visit will be followed until it resolves, the investigator assesses the subject's status to have returned to baseline, or until the investigator feels that the event is stable and chronic.

The investigator shall submit to the reviewing IRB a report of any UADE occurring during an investigation as soon as possible in accordance with the IRB submission guidelines, but in no event later than 10 working days after the investigator first learns of the effect.

12. INVESTIGATOR'S FILES/RETENTION OF DOCUMENTS

The investigator must maintain adequate and accurate records to enable the conduct of the study to be fully documented and the study data to be subsequently verified. These documents should be classified into two different separate categories (1) Investigator's Study File, and (2) Subject clinical source documents. The Investigator's Study File will contain the protocol/amendments, data collection forms, Independent Ethics Committee/Institutional Review Board and governmental approval with correspondence, sample informed consent, device records, staff curriculum vitae and authorization forms and other appropriate documents/correspondence. All records defined in 21 CFR 812.140 will be kept on file.

Subject clinical source documents include subject hospital/clinic records, physician's and nurse's notes, appointment book, original lab reports, special assessment reports, signed informed consent forms, subject screening and enrollment logs.

The investigator must keep these two categories of documents on file for at least 2 years after the latest of the following: completion, discontinuation of the study, or the regulatory submission for which the study is being performed is no longer under review. After that period of time the documents may be destroyed, subject to local regulations.

Should the investigator wish to assign the study records to another party or move them to another location, Regenesis Biomedical, Inc. must be notified in advance.

If the investigator cannot guarantee this archiving requirement at the investigational site for any or all of the documents, special arrangements must be made between the investigator and Regenesis Biomedical, Inc. to store these in a sealed container(s) off-site so that they can be returned sealed to the investigator in case of a regulatory audit. Where source documents are required for the continued care of the subject, appropriate copies should be made for storing outside of the site.

